10.3. Dose Modification

Dose Escalation

Following commencement of study treatment, patients are evaluated for response after 8 weeks (beginning at Week 9) and, if the patient has required one or more RBC transfusion in that period then the dose is increased by one dose level based on the body weight category. After each dose adjustment, the patient remains on the dose level for a minimum of 8 weeks before further adjustment is permitted based on the next scheduled visit.

Dose Reduction

The down titration of the study treatment is allowed at any time but must be performed if any of the following criteria are met. Hb levels should be retested for confirmation every 2 weeks after a dose reduction; however, it is per investigator's discretion:

- a. Transfusion independent for ≥ 56 days consecutively and Hb ≥ 12 g/dL; or
- b. Transfusion independent for ≥ 56 days consecutively and the rate of rise of Hb ≥ 2.5 g/dL over 4 weeks.
- c. In the instance where the patient achieved TI in the initial 8-weeks of the study, or has undergone treatment with the maximum allowable dose, i.e., 400 mg TIW or 3.5mg/kg for at least 8-weeks, patient may undergo dose reduction by 1-dose level. If there were no difference in erythroid response (same transfusion burden and Hb was unchanged) at this dose level for 8-weeks compared to another lower dose level, investigator may contact Sponsor's Medical Monitor to discuss another potential dose reduction.

Dose adjustment rules for patients who have TI for ≥ 56 Days (Maintenance Phase) can be referenced to [Section 19.1](#).

The number of dose escalations will be summarized descriptively.

The number and percentage of patients who exceed maximum dose will be summarized. The maximum dose of study medication is capped at 3.5 mg/kg per dose or 400 mg, whichever is lower.

The number and percentage of patients with a prescribed dose increase and decrease will be summarized. The number and percentage of patients with an actual dose hold, increase and decrease will be summarized.

The summaries above will be presented by every cumulative 4-weeks, e.g., up to 4 weeks, up to 8 weeks, ..., up to 52 weeks and up to 52 weeks and beyond.

Dose modifications by primary investigator or by patient collected on the eCRF will be listed. Hb level meeting the dose adjustment rules will be combined in the listing.

11. PRIOR AND CONCOMITANT MEDICATIONS

For open-label component, the summaries will be presented by dose level cohort.

For OL high-erythropoietin component, the summaries will be presented along with the cohorts from open-label component.

For double-blind component, the summarizes will be presented by treatment group.

The World Health Organization Drug Dictionary (WHODD) Version 2015 will be used to classify prior and concomitant medications by therapeutic class and preferred term based on ATC code level 3. Prior medication is defined as any medication taken and stopped prior to the first dose of the study medication. Concomitant medication is defined as any medication taken between the day of first dose of the study medication and the day of last study medication date + 28 days, inclusive.

Medication start and end dates will be compared with the start date of study drug and classified as per Table 3. In case of partial or missing dates, comparisons will be made based on the level of details available. For example, if start date of study drug administration is 04Jan2013, and a medication has a start date of 04Jan2013, the medication will be classified as concomitant. A start date of Jan2013 (i.e., missing day) would also see the medication classified as concomitant.

Table 3: Classification of Prior and Concomitant Medications

Start Date \ End date	Before start of study drug administration	On or after start of study drug administration	Missing
Before start of study drug administration	Prior	Concomitant	Concomitant
On or after start of study drug administration	N/A	Concomitant	Concomitant
Missing	Prior	Concomitant	Concomitant

Both prior and concomitant medication usage will be summarized by the number and proportion of patients receiving each drug within each therapeutic class using the safety population. Multiple drug usage in the same therapeutic class and preferred term by a patient will be counted only once.

A summary for prior ESA use and ESA Refractory, will be presented for double-blind component.

Detailed analyses may be performed on prior and concomitant medications of special interests such as oral iron, statin, phosphate binders and anticoagulants based on TLF shells.

Procedures and non-drug therapies will be summarized by the number and percentage. Detailed analyses may be performed on procedures and non-drug therapies of special interest such as bone marrow transplant.

12. EFFICACY ANALYSES

12.1. Multiple Comparisons/Multiplicity

For open-label component and OL high-erythropoietin component, there will be no statistical inference intended; hence, no multiplicity adjustment is needed.

For double-blind component, the statistical test results of the primary and secondary endpoints in the first 28-week treatment period (or at Week 28) and in the 52-weeks of treatment period (or at Week 52) will be used to determine treatment efficacy of roxadustat. To control the family-wise type I error at the alpha level of 0.05, a sequential gatekeeping procedure will be used to test the primary and secondary efficacy endpoints. Specifically, if the test of the primary endpoint is significant at the level of 0.05, the first secondary endpoint will be tested at the level of 0.05. Other secondary endpoints will be tested conditioning on the previous endpoint achieving the statistical significance, in the order listed in [Section 12.3.3](#). Statistical testing will stop at the first endpoint that fails to achieve the significance level. All statistical tests will be two-sided at the significance level of 0.05.

12.2. Analysis of Open-Label and OL High-Erythropoietin Data

For the Open-Label and OL high-erythropoietin component, the primary efficacy endpoint is the proportion of patients who were TI for ≥ 8 consecutive weeks during the first 28 treatment weeks. Secondary endpoints include TI ≥ 56 consecutive days anytime in the first 52 weeks of treatment, proportion of patients who achieved $\geq 50\%$ reduction in number of RBC transfusion over any 8 weeks compared to baseline, proportion of patients who achieved TI for > 20 weeks. These estimands are defined in Sections 12.3.1 and [12.3.3.2](#).

Because of the small sample sizes for the OL component and OL high erythropoietin component, descriptive analyses with frequency tables will be provided.

A frequency table of patients with at least a 50% reduction in the number of pRBC transfusions over any 8-week (56 consecutive days) period during the study as compared with the baseline will be provided by dose level cohort. Similar strategies as described in [Section 12.3.3.2](#) will be implemented for potential intercurrent events.

A frequency table of patients who achieved TI ≥ 56 consecutive days (e.g., 8 weeks) since first dose in the first 28-weeks of treatment will be provided by dose level cohort. TI is defined as the absence of any intravenous RBC transfusion (packed cell or whole blood) during any consecutive 56 days during the treatment period (e.g., Days 1 to 56, Days 2 to 57, Days 3 to 58). Similar strategies as described in [Section 12.3.1.1](#) will be implemented for potential intercurrent events.

A by-patient listing of transfusion records will also be provided.

12.3. Analysis of Double-Blind Efficacy Endpoints

12.3.1. Analysis of Primary Efficacy Endpoint

The primary efficacy endpoint for this study is proportion of patients who achieved TI ≥ 56 consecutive days (e.g., 8 weeks) since first dose in the first 28-week of treatment. TI is defined as the absence of any intravenous RBC transfusion (packed cell or whole blood) during any consecutive 56 days during the treatment period (e.g., Days 1 to 56, Days 2 to 57, Days 3 to 58). All RBC transfusions from 8 to 16 weeks prior to first dose until end of study will be recorded on CRF. TI will be estimated in the duration beginning with the first dose date (Day 1) and ending with the date of end of treatment or last visit date at

week 28, whichever comes earlier. RBC transfusions after end of treatment will be recorded on the CRF until the last visit at week 52 from first dose but will not be used to define TI.

The endpoint will be also analyzed for the end of the 52-week study treatment period as a secondary endpoint.

12.3.1.1. Primary Analysis

The RBC TI response rate and its two-sided 95% confidence interval based on the exact method of Clopper-Pearson will be presented in a frequency table by treatment group using the FAS.

The primary objective of the study will be evaluated to demonstrate a statistically significant difference between roxadustat and placebo group with respect to the RBC transfusion independence rate based on the Cochran-Mantel-Haenszel (CMH) chi-square test adjusting for the stratification factors (EPO level, IPSS-R risk category and RBC transfusion burden). A CMH-adjusted odds ratio (roxadustat versus placebo) and its associated 95% CI will be computed to compare between the roxadustat group and placebo group.

This analysis will take into account the potential intercurrent events as follows:

1. Treatment discontinuation (such as: due to Disease progression, Liver function, Patient decision, Investigator decision, AE/SAE, etc.): using while on treatment strategy: Patients who have discontinued treatment early for any reasons prior to week 8 will be classified as non-responders. For patients who have discontinued treatment early for any reasons after week 8, TI will be estimated in the duration beginning with the first dose date (Day 1) and ending with the date of end of treatment or last visit date at week 28, whichever comes earlier.
2. Death: using While on treatment strategy: Treatment effect while on treatment is of interest. Patients who died prior to week 8 will be classified as non-responders. For patients who died after week 8, the RBC TI response will be based on RBC transfusion records up to the date of end of treatment or last visit date at week 28 or death, whichever comes earlier.

The number of periods of 8 weeks (56 consecutive days) that meet the criterion of TI per TI responder will be summarized descriptively.

Hypothesis testing:

The odds ratio (OR) in treatment response (roxadustat vs. placebo) is given by:

$$OR = (n_1 * (N_2 - n_2)) / (n_2 * (N_1 - n_1))$$

Where:

N_1 = the number of patients in roxadustat group

N_2 = the number of patients in placebo group

n_1 = the number of patients who achieved TI \geq 56 consecutive days (e.g., 8 weeks) since first dose in the first 28-weeks of treatment in roxadustat group

n_2 = the number of patients who achieved TI \geq 56 consecutive days (e.g., 8 weeks) since first dose in the first 28-weeks of treatment in placebo group

The null and alternative hypotheses that will be tested at 2-sided significant level 5% are:

H_0 : OR = 1 versus H_a : OR \neq 1

The p-value from the stratified CMH chi-square test will be the confirmatory p-value for the test of the null hypothesis that the proportion of patients achieving RBC transfusion independence is equal between the two treatment groups.

SAS code for Cochran-Mantel-Haenszel (CMH) test

The two-sided CMH test will be performed using SAS procedure PROC FREQ with the CMH option in the TABLES statement. Baseline EPO level, IPSS-R risk category and RBC transfusion burden will be the stratification variables. The variables <reatment> and <response> determine the rows and columns of the tables.

Sample code:

```
PROC FREQ DATA = <input_dataset sorted> NOPRINT;  
    TABLES <strata_var>* <treatment_var> * <response_var> / CMH EXACT RISKDIFF;  
RUN;
```

Handling of missing values in primary analysis

Patients who have discontinued treatment early for any reasons prior to week 8 will be classified as non-responders. If significant differential treatment discontinuation prior to week 8 is observed between the two treatment groups, additional sensitivity analyses may be explored.

Sensitivity Analysis

Sensitivity Analysis 1: PPS Analysis

The primary analysis will be repeated using PPS as a sensitivity analysis.

Sensitivity Analysis 2: Logistic Regression Analysis

The primary analysis for primary endpoint will also be repeated using a multivariate logistic regression. The following variables/factors will be used in the model:

- treatment group (roxadustat vs. placebo);
- age group (< 65 vs. ≥65 years);
- centrally confirmed IPSS-R category (Intermediate vs. Low-risk/very low risk);
- transfusion burden (1 pRBC/8-weeks over 16 consecutive weeks vs. 2-4 pRBC/8-weeks);
- baseline hemoglobin
- baseline EPO level (≤200 mIU/mL vs. >200 mIU/mL and ≤400 mIU/mL);

In addition, MDS duration, baseline platelet counts, and bone marrow blasts will be also investigated as continuous variables.

A Wald test based on the estimated regression parameter for treatment group assignment will provide the basis for the hypothesis testing. The odds ratio (roxadustat versus placebo) and its 95% confidence interval will be provided. An example of the SAS code is displayed below:

```
PROC LOGISTIC;  
    CLASS <treatment_var> <factors>;  
    MODEL <response_var> = <treatment_var> <factors>;  
RUN;
```

An adjusted difference in proportions and its 95% Confidence Interval from the same logistic regression model will be presented using the method proposed by Ge et al. (2011). See [Appendix 19.7](#) for SAS sample code.

A swimming plot will be provided to display the RBC transfusions and TI periods during treatment period. The RBC TI response rates over longer periods (at least 8 consecutive weeks, at least 12 consecutive weeks, at least 16 consecutive weeks, and at least 20 consecutive weeks) during treatment will be plotted by treatment groups, in bar charts, with p-values calculated by the Cochran-Mantel-Haenszel (CMH) chi-square test adjusting for the stratification factors (EPO level, IPSS-R risk category and RBC transfusion burden).

The analyses in this section will use the FAS population.

12.3.2. Sequential Gatekeeping Procedure

Once the primary hypothesis has been rejected for the primary endpoint, the primary endpoint at week 52 and the secondary endpoints in the order specified in the Table 4 will be tested using a sequential gatekeeping procedure, in order to maintain the overall two-sided type I error of 0.05. If p-value from a test is < 0.05 , the claim of superiority will be considered successful, and the test will progress to the next comparison in sequence as follows.

Table 4: Sequential Gatekeeping Procedure

Test	Variable	Comparison
1	Proportion of patients who achieved TI ≥ 56 consecutive days (e.g., 8 weeks) since first dose in the first 28-weeks of treatment	Superiority of roxadustat versus placebo
2	Proportion of patients who achieved TI ≥ 56 consecutive days (e.g., 8 weeks) since first dose in the 52-weeks of treatment	Superiority of roxadustat versus placebo
3	Proportion of patients who achieved TI ≥ 56 consecutive days (e.g., 8 weeks) anytime during the study	Superiority of roxadustat versus placebo
4	Proportion of patients who achieved $\geq 50\%$ reduction in number of pRBC transfusions over 8 weeks compared to their Baseline for any 8-week period during the study	Superiority of roxadustat versus placebo
5	Cumulative number of patient-exposure-weeks (PEW) of TI over the first 28 weeks of the treatment period	Superiority of roxadustat versus placebo
6	Number of pRBC transfused change from baseline over the first 28 weeks of the treatment period	Superiority of roxadustat versus placebo
7	Proportion of patients who achieved TI for ≥ 20 consecutive weeks (140 consecutive Days)	Superiority of roxadustat versus placebo

8	Mean change from baseline in the PROMIS-SF v2.0 Physical Function 10b score at week 9	Superiority of roxadustat versus placebo
9	Mean change from baseline in the PROMIS-SF v1.0 Fatigue 13a score at week 9	Superiority of roxadustat versus placebo
10	Mean change from baseline in EQ-5D-5L VAS score at week 9	Superiority of roxadustat versus placebo

12.3.3. Analysis of Secondary Efficacy Endpoints

All secondary endpoints measured for treatment periods will be analyzed both for the first 28 weeks of treatment and for 52-week study treatment period. Others will be analyzed for the time during the study. The secondary efficacy endpoints will be analyzed based on the FAS population unless it is specified otherwise. Analyses using the PPS will be used as sensitivity analyses.

12.3.3.1. Proportion of Patients who achieved TI ≥ 56 consecutive days anytime during the study

The proportion of patients who achieved TI for ≥ 56 consecutive days will be summarized using the FAS and PPS and will be compared between the two treatment groups. TI is defined as the absence of any intravenous RBC transfusion (packed cell or whole blood) during any consecutive 56 days anytime during the study. TI will be estimated in the duration beginning with the first dose date (Day 1) and ending with the end of study or treatment discontinuation due to AE/SAE or death, whichever comes earlier. RBC transfusions after end of treatment will be recorded on CRF until the last visit at week 52 from first dose and will be used to define TI.

The p-value obtained will be reported for the test of the null hypothesis that there is no difference between the two treatment groups.

Similar methods will be used as for the primary endpoint.

This analysis will take into account the potential intercurrent events as follows:

1. Treatment discontinuation due to any reasons: using Treatment-policy strategy: regardless of these intercurrent events occurred; the TI will be estimated using RBC transfusion records in the whole study duration.
2. Death: using Treatment-policy strategy: regardless of these intercurrent events occurred; Patients who died prior to week 8 will be classified as non-responders. TI will be estimated using RBC transfusion records for the study duration up to death.

12.3.3.2. Proportion of Patients Who Achieved $\geq 50\%$ Reduction in Number of pRBC Transfusions over 8 Weeks Compared to Their Baseline for Any 8 Week Period during the Study (Factor of Erythroid Response)

See [Section 5.5](#) for the definition of number of pRBC (packs of red blood cells) transfusions at baseline. Percent change from baseline for any of the post-baseline 8-week period will be rounded to one decimal place (i.e., xx.x %) and then compared to 50% to determine whether the required percentage of reduction is achieved for that period. A frequency table of patients with at least a 50% reduction in the number of pRBC transfusions over any 8-week period in the duration beginning with the first dose date (Day 1) and ending with the end of study or treatment discontinuation due to AE/SAE or death, whichever comes earlier as compared with the baseline will be provided. The response rate and its two-sided 95% confidence intervals based on the exact method of Clopper-Pearson will be presented in the table by treatment group.

Treatment comparison will be based on the Cochran-Mantel-Haenszel (CMH) chi-square test, controlling for stratification factors (Serum EPO level, IPSS-R risk category and pRBC transfusion burden).

Two-sided 95% confidence interval (CI) of the odds ratio will also be presented.

The p value from the stratified CMH chi-square test will be provided for the test of the null hypothesis that the proportion of patients with at least a 50% reduction is equal between the two treatment groups.

The number of periods of 8 weeks (e.g., consecutive 56 days) per responder will be summarized descriptively.

This analysis will take into account the potential intercurrent events as follows:

1. Treatment discontinuation due to reasons: using Treatment-policy strategy: regardless of these intercurrent events occurred; the RBC transfusion reduction will be estimated using RBC transfusion records in the whole study duration.
2. Death: using Treatment-policy strategy: regardless of these intercurrent events occurred;. Patients who died prior to week 8 will be classified as non-responders. RBC transfusion will be estimated for any 8-week period in the study duration up to death.

PPS analysis will be used as sensitivity analysis.

12.3.3.3. Cumulative Number of Patient-Exposure-Weeks (PEW) of TI over the first 28 Weeks of the Treatment Period

The cumulative number of patient-exposure-weeks per patient of TI over the first 28-weeks of the treatment period will be summarized and analyzed using the FAS and PPS population.

The exposure time will be measured using patient-exposure-week (PEW). PEW of TI periods over the first 28-weeks will be added up to a cumulative number of weeks. For a patient with at least one TI response period over the first 28-weeks, the last TI response period will end with the date of a subsequent RBC transfusion, visit date at week 28, date of the end of study or treatment discontinuation due to AE/SAE or death, whichever comes earlier. For a patient with no TI response period over the first 28 weeks, the cumulative number of PEW will be set to zero.

The cumulative number of PEW over the first 28 weeks of treatment period will be summarized using descriptive statistics by treatment group. Treatment comparison will be based on a non-parametric ANCOVA (stratified rank ANCOVA) described in Stokes, Davis, and Koch 2000. The analysis will use baseline hemoglobin as covariate, treatment arm as fixed effects, controlling for stratification factors (baseline endogenous EPO level, IPSS-R risk category and RBC transfusion burden). See [Section 5.5](#) for the definition of number of pRBC (packs of red blood cells) transfusions at baseline.

Since it is expected that the sample sizes are not large for all strata, the following steps and SAS codes are to be used:

Step 1: Compute the ranks of the response variable and covariate across the two treatment groups.

Sample SAS code:

```
PROC RANK TIES = mean OUT = ranks;  
  BY <strata_var>;  
  VAR <baseline_var> <response_var>;  
RUN;
```

Step 2: With the ranks of response variable, an ANCOVA model will be fitted including the baseline ranks and stratification factor as covariates.

Sample SAS code:

```
PROC MIXED DATA = ranks;
  CLASS <strata_var>;
  MODEL <R_response_var> = <R_Baseline_var> <strata_var>/OUTP = res;
RUN;
```

Step 3: CMH mean score statistics will be used to compare the two treatment groups using the values of the residuals obtained from step 2 as scores. The p-value obtained will be reported.

Sample SAS code:

```
PROC FREQ DATA = res;
  TABLES <strata_var>* <treatment_var>*resid/CMH2;
RUN;
```

The p-value from the stratified CMH chi-square will be provided for the test of the null hypothesis that there is no difference in two treatment groups.

Week 28 and week 52 are the analysis endpoint for 28-week and 52-week analysis respectively.

This analysis will take into account the potential intercurrent events as follows:

1. Treatment discontinuation (such as: due to Disease progression, Liver function, Patient decision, Investigator decision, AE/SAE, etc.): using While on treatment strategy: PEW of TI will be estimated in the duration beginning with the first dose date (Day 1) and ending with the date of end of treatment or last visit date at week 28/52, whichever comes earlier.
2. Death: using While on treatment strategy: Treatment effect while on-treatments of interest. PEW of TI will be based on RBC transfusion records up to the date of end of treatment or last visit date at week 28/52 or death, whichever comes earlier.

In addition, the cumulative number of Patient-Exposure-Weeks of TI at week 28 and week 52 will be also summarized using the box-whisker plot by treatment groups.

12.3.3.4. Number of pRBC Transfused compared to Baseline over the first 28 Weeks of the Treatment Period

Descriptive statistics of the number (pRBC/8 weeks) of pRBC transfused and number (pRBC/8 weeks) of pRBC transfused change from baseline will be presented by treatment group using FAS and PPS. See [Section 5.5](#) for the definition of number of pRBC transfusions at baseline.

Treatment comparison will be performed for the number (pRBC/8 weeks) of pRBC transfused change from baseline based on a non-parametric ANCOVA (stratified rank ANCOVA) using baseline hemoglobin and baseline pRBC transfusions (pRBC/8 weeks) as covariate, treatment arm as fixed effects, controlling for stratification factors baseline endogenous EPO level and IPSS-R risk category. The p-value obtained will be reported for the test of the null hypothesis that there is no difference in two treatment groups.

Week 28 and week 52 are the analysis endpoint for 28-week and 52-week analysis respectively.

Similar methods will be used as in [Section 12.3.3.3](#). Similar Strategies will be implemented for potential intercurrent events.

12.3.3.5. Proportion of Patients Who Achieved TI for ≥ 20 consecutive Weeks (140 consecutive Days) anytime during the study

The proportion of patients who achieved TI for ≥ 20 Weeks (140 Days) will be summarized using the FAS and PPS and will be compared between the two treatment groups. TI is defined as the absence of any intravenous RBC transfusion (packed cell or whole blood) during any consecutive 140 days anytime during the study. TI will be estimated in the duration beginning with the first dose date (Day 1) and ending with the end of study or treatment discontinuation due to AE/SAE or death, whichever comes earlier. RBC transfusions after end of treatment will be recorded on CRF until the last visit at week 52 from first dose and will be used to define TI.

The p-value obtained will be reported for the test of the null hypothesis that there is no difference between the two treatment groups.

Similar methods will be used as in [Section 12.3.3.1](#). Similar strategies will be implemented for potential intercurrent events.

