4.2.2. Definition of Estimand for Secondary Efficacy Endpoints

Population of interest: The same population as defined in Primary Efficacy Endpoint.

Table 1: Other Estimand Attributes for Secondary Efficacy Endpoints

Table Endpoint of interest	Population-level summary for the endpoint	Handling of intercurrent events	
		Treatment discontinuation*	Death
RBC TI (transfusion independence) response defined as if patients achieved TI \geq 56 consecutive days in the first 52 weeks of treatment.	Odds ratio of patients who achieved transfusion TI \geq 56 consecutive days in the first 52 weeks of treatment between treatment and placebo arm.	While on treatment strategy: response to treatment prior to the occurrence of treatment discontinuation	While on treatment strategy: response to treatment prior to death.
RBC TI (transfusion independence) response defined as if patients achieved TI \geq 56 consecutive days anytime during the study	Odds ratio of patients who achieved transfusion TI \geq 56 consecutive days anytime during the study between treatment and placebo arm	Treatment-policy strategy: regardless of these intercurrent events occurred;	Treatment-policy strategy: regardless of these intercurrent events occurred.
Reduction in number of pRBC transfusions over 8 weeks compared to their baseline for any 8-week period during the study	Odds ratio of patients who achieved \geq 50% reduction in number of pRBC transfusions over 8 weeks compared to their baseline for any 8-week period during the study between treatment and placebo arm	Treatment-policy strategy: regardless of these intercurrent events occurred;	Treatment-policy strategy: regardless of these intercurrent events occurred.
Patient-exposure-weeks (PEW) of TI over the first 28 weeks of the treatment period	Difference in PEW of TI over the first 28 weeks of the treatment period between treatment and placebo arm	While on treatment strategy: treatment effect prior to the occurrence of treatment discontinuation	While on treatment strategy: Treatment effect while on treatment
Number of pRBC packs transfused compared to baseline over the first 28 weeks of the treatment period	Difference in mean of pRBC transfused change from baseline over the first 28 weeks of the treatment period between treatment and placebo arm	While on treatment strategy: treatment effect prior to the occurrence of treatment discontinuation	While on treatment strategy: Treatment effect while on-treatment

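### Gatekept Tests 3, 4 and 7 are declared treatment-policy but derived with follow-up cut at AE discontinuation, and Test 5 has the reverse conflict

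*SAP*

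**What the plan says.** SAP Section 4.2.2, Table 1, assigns Tests 3, 4 and 7 one strategy for treatment discontinuation: "Treatment-policy strategy: regardless of these intercurrent events occurred". The table's footnote names AE/SAE among the discontinuation reasons covered.

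For Test 3, Section 12.3.3.1 sets the window from Day 1, "ending with the end of study or treatment discontinuation due to AE/SAE or death, whichever comes earlier". Its first intercurrent-event item then covers discontinuation for any reason and states that "the TI will be estimated using RBC transfusion records in the whole study duration". The section also says that transfusions recorded after end of treatment, up to Week 52, count towards TI.

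For Test 4, Section 12.3.3.2 repeats the cut, "ending with the end of study or treatment discontinuation due to AE/SAE or death, whichever comes earlier as compared with the baseline", and then says "the RBC transfusion reduction will be estimated using RBC transfusion records in the whole study duration".

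For Test 7, Section 12.3.3.5 repeats the cut and takes its strategies from Section 12.3.3.1 by reference.

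For Test 5 (PEW), Table 1 declares while-on-treatment. The derivation in Section 12.3.3.3 closes the last TI period at the earliest of the next transfusion, the Week 28 visit, or the "date of the end of study or treatment discontinuation due to AE/SAE or death, whichever comes earlier". The intercurrent-event item in the same section instead stops the count when drug is stopped, or at the Week 28/52 visit if that is earlier; it opens "PEW of TI will be estimated in the duration beginning with the first dose date (Day 1) and ending with the date of end of".

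**The concern.** A patient who stops for an AE cannot both lose and keep later follow-up. If the derivation is programmed as written, the recorded reason for stopping decides whether later transfusion data count. That reason is partly a matter of judgement, since Protocol Section 4.3 lists AE, patient decision, investigator decision and lack of efficacy as separate reasons. The mix of reasons may also differ by arm.

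In Test 5 the same cut works the other way. A patient who stops for lack of efficacy or by own decision can keep accruing TI weeks off drug, although the estimand is limited to time on drug.

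All four endpoints sit in the fixed sequence of SAP Table 4, which stops at the first failure. A sponsor group is unblinded at Week 28, before the secondary tests are run. If the windows are still open then, either result could be presented as the pre-specified one.

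**Working it through.** **Text comparison**

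| Test | SAP section | Window in the derivation | Declared strategy |
|---|---|---|---|
| 3 | 12.3.3.1 | Ends at AE/SAE discontinuation, death or end of study | Treatment policy, any reason, whole study |
| 4 | 12.3.3.2 | Same | Treatment policy, whole study |
| 7 | 12.3.3.5 | Same | Treatment policy (Table 1; 12.3.3.1 by reference) |
| 5 | 12.3.3.3 | Of all discontinuations, only AE/SAE ends the last TI period | While on treatment |

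The PRO rows of Table 1 separate AE/SAE from other reasons; the transfusion rows do not. So the SAP makes an AE exception explicitly when it wants one. The AE cut also recurs in Sections 12.3.4.1 to 12.3.4.3, and 12.3.4.3 cites 12.3.3.1 for it. Nothing in the documents says which text prevails.

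**Do the two windows hold different data?** Yes. Patients who stop drug for any reason stay in the study to Week 52 (Protocol 4.3, SAP 3.1), with transfusions recorded. Week 52 is day 52 × 7 = 364. Under the whole-study rule a 56-day run can start as late as day 364 − 56 + 1 = 309, and a 140-day run as late as day 364 − 140 + 1 = 225. Under the AE cut, a patient who stops for an AE before day 56 (Tests 3 and 4) or day 140 (Test 7) cannot respond. Because any qualifying run counts, the whole-study rule can only add responders, in either arm.

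For Test 5, a patient who stops at week *w* for a non-AE reason can gain up to 28 − *w* weeks under the derivation that the while-on-treatment rule excludes.

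**Size.** The SAP states no sample size, power or rates for these tests, so there is no planned figure to reproduce. SAP 3.2 gives rates for the primary endpoint only: 35% vs 5% at N = 160 and 56% vs 13% at N = 120. Exact Fisher power is 99.9% in both cases, consistent with the stated minimum of 90%.

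Inputs for the illustration:
- 140 patients enrolled (SAP 17) at 3:2 (SAP 3.3), so 140 × 3/5 = 84 and 140 × 2/5 = 56. The split is assumed.
- From SAP 12.1: "All statistical tests will be two-sided at the significance level of 0.05".
- Responder counts are assumed.

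The single-stratum CMH statistic, with *x* roxadustat responders and *m* responders in total, is Q = (x − e)²/v, where e = 84m/140 and v = 84 × 56 × m(140 − m)/(140² × 139).

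- 40/84 vs 18/56: m = 58, e = 34.8, v = 8.212, Q = 5.2²/8.212 = 3.293, p = 0.070 (Fisher 0.081).
- 42/84 vs 18/56: m = 60, e = 36.0, v = 8.288, Q = 6.0²/8.288 = 4.344, p = 0.037 (Fisher 0.039).

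The same formula with other assumed counts:

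| AE cut | Whole study | CMH p, AE cut | CMH p, whole study |
|---|---|---|---|
| 40/84 vs 18/56 | 42/84 vs 18/56 | 0.070 | 0.037 |
| 34/84 vs 14/56 | 35/84 vs 14/56 | 0.060 | 0.044 |
| 25/84 vs 8/56 | 25/84 vs 9/56 | 0.035 | 0.065 |
| 29/84 vs 3/56 (35%/5%) | 29/84 vs 7/56 | 0.00006 | 0.0036 |
| 47/84 vs 7/56 (56%/13%) | 47/84 vs 11/56 | <0.0001 | <0.0001 |

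One or two reclassified patients move a borderline result across 0.05, in either direction. A large effect is not moved.

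**The case against.** The strongest reply concerns size and reach.

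- **Conditional difference.** For Tests 3, 4 and 7 the rules coincide for everyone except AE discontinuers, and the p-value moves only if one of them first qualifies on days after stopping. This stands.
- **Assumed counts.** At the SAP's re-estimated primary rates, even 47/84 vs 15/56 gives p = 0.0007. Those rates belong to another endpoint, but they are the only ones available. No AE-stop rate is given, and Protocol 2.6 says the drug effect reverses when treatment stops. This limits the likely size.
- **Tests 1 and 2 come first.** The AE-cut window contains the Test 2 on-treatment window. For Test 3 to fail at 40 vs 18 after Test 2 succeeds, placebo must gain an off-drug responder. That can happen: 40 vs 17 gives p = 0.042.
- **Test 5 is less evenly balanced.** SAP 5.7 ends the treatment period at the last dose, which favours the on-treatment reading. The derivation sentence still names AE/SAE as the only discontinuation that closes the last TI period, so it needs correcting.
- **The cut may be intended.** It recurs often enough to be deliberate. In that case Table 1 and the strategy text are wrong, and the contradiction remains.
- **Limited exposure.** Investigators are blinded, which limits arm-dependent coding of reasons, though AE rates may still differ by arm. Week 28 efficacy testing covers only the primary endpoint, but the output list in SAP 19.9 includes a PEW figure that depends on the disputed Test 5 derivation.

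These points bear on how large the effect may be, not on whether the definitions conflict.

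**Conclusion.** The concern holds. Tests 3, 4 and 7 each have two incompatible windows, and the AE cut does not estimate what Table 1 declares. Test 5 has the opposite mismatch. The primary analysis and Test 2 are unaffected.

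The size cannot be fixed from the documents, and the direction of any bias depends on which arm has more AE stops followed by transfusion-free periods. Under the assumed 84:56 split, one or two patients decide a borderline test, and a failure at Test 3 leaves Tests 4 to 10 untested. With effects near 35% vs 5% or 56% vs 13%, the decision on these responder tests would not change. It must be fixed because confirmatory tests in a fixed sequence need one definition each before unblinding.

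**What to change.** In SAP 12.3.3.1, 12.3.3.2 and 12.3.3.5, delete AE/SAE discontinuation as a stopping point, so that the window ends at end of study or death, as Table 1 implies. In 12.3.3.3, end the last TI period at the earliest of the next transfusion, the Week 28 visit, end of treatment for any reason, or death. Section 12.3.3.4 (Test 6) borrows its methods from 12.3.3.3, so confirm that it takes the corrected window. Carry the whole-study window into the censoring rules of 12.3.4.1 to 12.3.4.3.

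If the AE cut is deliberate, rewrite Table 1 and the strategy text instead and drop the treatment-policy label. In either case, keep the other window as a named sensitivity analysis. The first option is preferable because it delivers the estimands already declared.

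The cost is SAP wording and one derivation change, made before database lock and any unblinding. No new data are needed, since transfusions are already recorded to Week 52.
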